9.1 Sample Size Justification

Assuming baseline NIV failure/intubation rate of 50%, a 30% absolute reduction requires 20 patients for 80% power at $\alpha=0.05$ (two-sided). Interim analysis after 10 patients will assess safety and futility.

9.2 Analysis Populations

- **Intent-to-Treat (ITT):** All enrolled patients who received any study intervention.
- **Per-Protocol (PP):** Patients completing at least 2 hours of sedation without major protocol violations.

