Study Protocol and Statistical Analysis Plan

Isoflurane Sedation Using AnaConDa® Device with Non-Invasive Ventilation for Acute Exacerbation of COPD

**Protocol version 2.0
Dated 04.12.2022**

1. Protocol Synopsis

Title	Isoflurane Sedation Using AnaConDa® Device with Non-Invasive Ventilation for Acute Exacerbation of COPD
Study Design	Prospective, single-arm, interventional pilot study
Study Population	Adult patients (≥ 18 years) with acute exacerbation of COPD requiring NIV
Sample Size	20 patients (interim analysis after 10 enrollees; final analysis planned on 20)
Intervention	Isoflurane sedation via AnaConDa® device during NIV
Primary Objective	Incidence of intervention failure (intubation or excessive sedation)
Secondary Objectives	Safety (vitals, ABG changes), sedation depth (RASS), patient comfort (VAS)
Duration	24 hours of sedation monitoring; follow-up until discharge or intubation
Ethics Approval	BREC 23/121 (20.03.2023), in accordance with ICH-GCP and Declaration of Helsinki

2. Background and Rationale

Acute exacerbations of COPD (AE-COPD) frequently lead to hypercapnic respiratory failure, where non-invasive ventilation (NIV) reduces intubation and mortality risks. However, NIV intolerance due to agitation or dyssynchrony often necessitates invasive ventilation, with attendant complications. Volatile anesthetics like isoflurane, delivered via AnaConDa®, offer rapid, titratable sedation with bronchodilatory effects and minimal accumulation. Preliminary ICU studies suggest improved hemodynamics and faster recovery with inhalational sedation, but data in the NIV setting are lacking. This pilot protocol aims to assess feasibility and safety of isoflurane sedation via AnaConDa® in AE-COPD on NIV.

3. Objectives

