3.1 Primary Objective

- Evaluate the incidence of intervention failure, defined as either requirement for endotracheal intubation or occurrence of excessive sedation (RASS ≤ -3).

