9.3 Primary Outcome Analysis

- Calculate proportion of intervention failures in ITT population.
- 95% confidence interval (CI) using Wilson's method.

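### The set labelled ITT in section 9.2 is a treated set, so a patient intubated before the intervention starts may drop out of the primary failure proportion

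*Combined protocol and SAP*

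**What the plan says.** Section 9.2 (Analysis Populations) gives the ITT set as "All enrolled patients who received any study intervention". Its only other set, per-protocol, requires at least 2 hours of sedation. Section 9.3 (Primary Outcome Analysis) then instructs: "Calculate proportion of intervention failures in ITT population", with a "95% confidence interval (CI) using Wilson's method".

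Section 3.1 describes failure as "defined as either requirement for endotracheal intubation or occurrence of excessive sedation", the latter being RASS of -3 or below. Nothing there requires that the drug has been started. The synopsis names the intervention as "Isoflurane sedation via AnaConDa® device during NIV". Section 4 (Study Design) puts isoflurane after consent and does not give the length of the gap.

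Section 9.1 starts from "Assuming baseline NIV failure/intubation rate of 50" per cent and states that "a 30% absolute reduction requires 20 patients". Section 2 says the pilot "aims to assess feasibility and safety of isoflurane sedation". No section says how a patient who was enrolled but never started is counted, reported or replaced.

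**The concern.** An intention-to-treat set normally holds everyone enrolled. This one adds a condition that is met only after enrolment, and in a severely ill population a patient can reach the endpoint before meeting it. Intubation between consent and drug start is a failure by section 3.1, yet the set used in section 9.3 can remove that patient from both numerator and denominator.

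The primary estimate may therefore be selected on an event related to the outcome. In a trial of 20 patients, each patient moves the proportion by several percentage points. The plan also has no place to report patients in whom the intervention could not be started, although section 2 names feasibility as an aim.

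**Working it through.** **1. Which set holds which patient.** Take isoflurane as the intervention, as in the synopsis.
- Started, later intubated: in ITT, counted as a failure.
- Intubated before start: meets section 3.1, but is in neither ITT nor per-protocol.
- Never started, not intubated: in neither set.

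**2. The plan's own figure.** Inputs from section 9.1: p0 = 0.50, p1 = 0.50 − 0.30 = 0.20, two-sided alpha 0.05, power 80%. For one proportion against a fixed value:

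n = [1.96 × √(0.5 × 0.5) + 0.8416 × √(0.2 × 0.8)]² / 0.30² = (0.980 + 0.3366)² / 0.09 = 19.26, rounded up to 20.

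Exact binomial check: the rule of at most 5 failures in 20 has probability 0.0207 at a true rate of 50% and 0.804 at 20%. The 20 patients reproduce, as a one-sample comparison with a fixed 50%. There is no allowance for patients lost before start.

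**3. Direction.** With x failures among n enrolled:
- dropping one failure changes x/n to (x−1)/(n−1), a fall of (n−x)/[n(n−1)];
- dropping one non-failure changes x/n to x/(n−1), a rise of x/[n(n−1)].

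For x = 6 and n = 20 the fall is 14/380 = 3.7 percentage points. For x = 5 the rise from one dropped non-failure is 5/380 = 1.3 points.

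**4. Size, on assumed numbers.** The documents give no number never started, so I take 20 enrolled, no replacement, and one or two pre-start intubations. The Wilson limits are

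[p + z²/(2n) ± z√(p(1−p)/n + z²/(4n²))] / (1 + z²/n), with z = 1.96.

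- 6/20: (0.3960 ± 0.2226)/1.1921 = 0.145 to 0.519.
- 5/19: (0.3642 ± 0.2223)/1.2022 = 0.118 to 0.488.

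| Failures in 20 enrolled | None dropped | One pre-start intubation dropped | Two dropped |
|---|---|---|---|
| 4 | 4/20 = 20.0% (8.1–41.6) | 3/19 = 15.8% (5.5–37.6) | 2/18 = 11.1% (3.1–32.8) |
| 5 | 5/20 = 25.0% (11.2–46.9) | 4/19 = 21.1% (8.5–43.3) | 3/18 = 16.7% (5.8–39.2) |
| 6 | 6/20 = 30.0% (14.5–51.9) | 5/19 = 26.3% (11.8–48.8) | 4/18 = 22.2% (9.0–45.2) |
| 7 | 7/20 = 35.0% (18.1–56.7) | 6/19 = 31.6% (15.4–54.0) | 5/18 = 27.8% (12.5–50.9) |

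Only the row with 6 failures changes whether the interval includes 50%. At 5 or fewer it is excluded already; at 7 it stays included. Three dropped at 7/20 would be needed to exclude it: 4/17 = 23.5% (9.6–47.3).

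**5. The opposite case.** Dropping never-started patients who were not intubated turns 5/20 = 25.0% (11.2–46.9) into 5/19 = 26.3% (11.8–48.8) for one patient, or 5/18 = 27.8% (12.5–50.9) for two. Two such patients would bring 50% back into the interval.

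**The case against.** The case on the other side has four parts.

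- **The criterion is any study intervention, not isoflurane.** Section 6 (Intervention) also covers device placement, fresh gas flow and NIV settings. On that reading a patient intubated during set-up stays in the set. This stands as an ambiguity: the synopsis supports the narrower reading, and section 9.2 does not choose between them.
- **A treated set suits the endpoint.** There is no randomisation to preserve, excessive sedation from isoflurane cannot precede isoflurane, and section 7 first records failure at 2 hours. This stands in part. A treated set is defensible in a single-arm pilot if it is called that. But intubation is the other half of the endpoint, and it can precede drug start.
- **The effect may be nil.** The gap from consent to start could be very short. This stands, and the documents do not settle it.
- **Feasibility is mentioned only in the background.** Sections 3.1 and 3.2 list no feasibility endpoint. This stands, so feasibility is a supporting reason and not the main one.

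A reader might go further and infer that the set makes isoflurane look better against the 50% rate. The documents do not support that. Section 9.3 plans no formal test or success rule against 50%; the comparison is only implied by section 9.1. Section 9.1 gives no source or time window for its rate, so whether that rate includes failures before sedation would start is unknown. The direction also depends on who fails to start, as step 5 of the working shows.

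**Conclusion.** The point holds in a limited form. The ITT label is wrong for the set defined, and on the synopsis's reading of the intervention the rule removes pre-start intubations that meet the plan's own failure definition. Each such removal lowers the primary estimate; in the table the fall is 3.4 to 4.7 percentage points per patient (7/20 to 6/19 at the low end, 4/20 to 2/18 via 3/19 at the high end). With one or two removed from 20 enrolled, the reading against 50% changes only at 6/20.

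This rests on assumed counts of never-started patients, on 20 enrolled without replacement, and on isoflurane being the qualifying intervention. If every enrolled patient starts, nothing changes. A biased primary result is not established; an avoidable route to selection, and an unclear set definition, are. The priority is low, but so is the cost of repair.

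**What to change.** In section 9.2:
- rename the current set *treated set*;
- state what counts as having received any study intervention (isoflurane started, or device and circuit fitted);
- define ITT as all consented, eligible enrolled patients.

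In section 9.3:
- report the failure proportion with its Wilson interval in all enrolled patients, counting intubation before the intervention starts as failure;
- give the treated-set figure beside it;
- report the number never started, with reasons.

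The cost is SAP wording and recording of outcomes for the few untreated patients. The stated failure proportion may be slightly less favourable. No clinical procedure changes.

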9.3 Primary Outcome Analysis

- Calculate proportion of intervention failures in ITT population.
- 95% confidence interval (CI) using Wilson's method.

9.4 Secondary Outcomes

- Continuous variables (vitals, ABG, RASS, VAS):
Summarize as mean \pm SD or median (IQR) as appropriate.
Paired t-test (or Wilcoxon signed-rank) comparing baseline vs. each time point.
- Categorical variables (intubation, excessive sedation):
Chi-square or Fisher's exact test.
- Time-to-intubation: Kaplan–Meier curve with log-rank test.

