3.2 Secondary Objectives

- Monitor changes in vital signs and arterial blood gas (ABG) parameters at baseline, 2, 6, 12, and 24 hours.

- Assess sedation depth using the Richmond Agitation-Sedation Scale (RASS) at the same time points.
- Measure patient comfort during NIV via Visual Analogue Scale (VAS, 0–10).

4. Study Design

This single-center, prospective interventional pilot study will enroll consecutive AE-COPD patients requiring NIV. After informed consent, eligible patients receive isoflurane sedation via AnaConDa® integrated into a dual-limb NIV circuit. Continuous safety monitoring will guide dose titration. An interim analysis after 10 patients will inform potential early termination for futility or safety concerns.

5. Study Population

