5.2 Exclusion Criteria

- Hypersensitivity to isoflurane or volatile anesthetics
- History of malignant hyperthermia
- Severe hepatic dysfunction
- Contraindications to NIV (e.g., facial trauma, uncontrolled secretions)
- GCS $<$ 12 or inability to protect airway
- Hemodynamic instability unresponsive to fluids
- Pregnancy or recent upper airway surgery/tracheostomy

6. Intervention

Isoflurane infusion will be initiated at 1.5 mL/h via syringe pump (Infusia SP7s®, Fresenius Kabi). The AnaConDa® device is placed between mask and ventilator Y-piece, with scavenging on expiratory limb. Fresh gas flow (FGF) is set at patient minute ventilation plus 0.5 L/min. Target $F_{et}\%$ (end-tidal concentration) is 0.3–0.5 vol% for light sedation. NIV settings:

- Pressure support: 8–20 cm H₂O (titrated to 10 mL/kg IBW)
- PEEP: 4–6 cm H₂O
- RR: 12–16 breaths/min (I:E 1:3–1:4)
- FiO_2 : 30–40% (titrate to SpO_2 88–94%)

Sedation depth will be adjusted based on RASS, targeting -1 to -2 . Excessive sedation ($\text{RASS} \leq -3$) prompts immediate cessation (failure event).

7. Study Assessments

Assessment	Baseline	2 h	6 h	12 h	24 h
Vital signs (HR, BP, RR)	✓	✓	✓	✓	✓
ABG parameters	✓	✓	✓	✓	✓
RASS	✓	✓	✓	✓	✓
VAS comfort score	✓	✓	✓	✓	✓
Intervention failure	—	✓	✓	✓	✓

8. Safety Monitoring

- Continuous pulse oximetry, ECG, non-invasive BP every 15 minutes for first hour, hourly thereafter.
- Monitor for hypotension ($\text{SBP} < 90 \text{ mmHg}$), bradycardia ($\text{HR} < 50 \text{ bpm}$), respiratory depression ($\text{RR} < 10 \text{ breaths/min}$).
- ABG review for hypercapnia or hypoxemia.
- Report serious adverse events (SAEs) within 24 hours to DSMC.

9. Statistical Analysis Plan

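### Section 9.4 plans about 28 to 40 unadjusted baseline comparisons and no confidence interval for any change, although changes in vitals and blood gases are the stated secondary safety objective (minor)

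*Combined protocol and SAP*

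**What the plan says.** Section 3.2 sets the secondary aim: "Monitor changes in vital signs and arterial blood gas (ABG) parameters at baseline, 2, 6, 12, and 24 hours", with RASS at the same times and VAS comfort as well. The synopsis lists vitals and ABG changes under safety, first among the secondary objectives.

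Section 9.4 gives the analysis: a mean with SD or median with IQR, and then "Paired t-test (or Wilcoxon signed-rank) comparing baseline vs. each time point". The table in section 7 names heart rate, blood pressure and respiratory rate as the vital signs and puts every measure at 2, 6, 12 and 24 h. It does not list the ABG values. The nearest guide is section 8, which asks for "ABG review for hypercapnia or hypoxemia".

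The documents give no significance level for section 9.4, no multiplicity rule, no key variable or time, no rule for choosing between the t-test and the Wilcoxon test, and no statement that the tests are exploratory. A confidence interval is planned only for the primary proportion (section 9.3).

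**The concern.** Two separate problems follow from a plan built on p-values alone.

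First, with several variables each tested at four times, an isolated result below 0.05 is easy to obtain when nothing has changed. The plan does not tell the reader how to weigh it.

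Second, and more important for a small safety-oriented pilot, a non-significant change in blood pressure, respiratory rate or PaCO2 could be taken as reassurance. Only an interval shows how large a deterioration the data still allow. It cannot be rebuilt from means and SDs at each time, because it needs the SD of the within-patient change.

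**Working it through.** **The plan's own figure.** The documents state no number of secondary tests and no familywise error rate. The one figure to reproduce is the sample size in section 9.1: 50% against 20% failure, 80% power, two-sided 0.05. The one-sample formula gives n = [(1.960 × √(0.5 × 0.5) + 0.842 × √(0.2 × 0.8)) / 0.30]² = 19.26, rounded up to 20. It reproduces, and N = 20 is used below.

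**Number of tests.** Tests = (3 vitals + k ABG values + RASS + VAS) × 4 times, with blood pressure counted once.

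- k = 2 (carbon dioxide and oxygenation, the least that section 8 implies): 7 × 4 = 28
- k = 3: 8 × 4 = 32
- k = 4: 9 × 4 = 36
- k = 5: 10 × 4 = 40

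Splitting blood pressure into systolic and diastolic adds four tests.

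**Chance of at least one false positive if nothing changes.** The 0.05 level is an assumption here; the documents state it only for the sample size. Expected false positives are 28 × 0.05 = 1.4 to 32 × 0.05 = 1.6. If all tests were independent, the chance of at least one would be 1 − 0.95^28 = 0.76 to 1 − 0.95^32 = 0.81. They are not independent, because the four tests on a variable share one baseline. Simulated paired t-tests (20 complete patients, correlation 0.5 between times, all nulls true) give:

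| Tests | Correlation between variables 0 | 0.3 | 0.5 |
|---|---|---|---|
| 28 | 0.70 | 0.66 | 0.59 |
| 32 | 0.75 | 0.70 | 0.63 |

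For 40 tests the results are 0.83 and 0.76 at correlations 0 and 0.3. For 32 tests, the chance of two or more false positives is 0.37 to 0.45, so less likely than not.

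**If some variables truly change.** Only true nulls can give false positives. One unchanged variable tested at four times gives about 0.16. Three unchanged variables (12 tests) give about 0.37 to 0.40 at correlations 0.5 to 0. If only RASS and VAS change, the 20 to 24 vitals and ABG tests that remain give about 0.49 to 0.64.

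**What a non-significant result leaves open.** The half-width of the 95% interval for a mean change, in SDs of the change, is t(0.975, n − 1)/√n:

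- n = 20: 2.093/√20 = 0.47
- n = 16: 2.131/√16 = 0.53
- n = 10: 2.262/√10 = 0.72

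The smaller numbers are illustrations. They are the pairs left at 24 h if every failure ended assessment at the 20% or 50% rates of section 9.1: 20 × 0.80 = 16 and 20 × 0.50 = 10. The synopsis ends follow-up at discharge or intubation, and the carry-forward rule in section 9.5 covers RASS and VAS only, so some loss of vitals and ABG pairs is plausible.

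**The case against.** The best case for leaving section 9.4 alone is that this is a single-arm pilot whose primary result is a proportion with a Wilson interval, and no success or stopping decision uses a secondary p-value. Safety also rests on excessive sedation within the primary endpoint, the vital-sign thresholds and serious adverse event reporting in section 8, and the DSMC review in section 9.6. The plan tests every time point, so selective reporting is a possibility and not something it invites. All of this stands and is why the point is minor. It does not supply the missing intervals, and pilot status argues for estimation over testing.

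The all-null premise is also open to challenge. Patients in hypercapnic failure start NIV and receive a sedative titrated to a RASS target. RASS is meant to move, and respiratory rate, PaCO2, pH and comfort may well move too. That stands: the 0.59 to 0.75 range is conditional, and with three unchanged variables a false positive is less likely than not.

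A reader might infer three stronger things that the documents do not support:

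- **A minimum of 32 tests.** That needs three ABG values, which are nowhere listed. The supported floor is 28.
- **A false-positive chance of 0.81.** That needs 32 independent tests, and these share baselines.
- **A need for formal multiplicity control.** Nothing in the documents ranks one contrast above the others. Holm within each variable would still leave up to 1 − 0.95^8 = 0.34 across eight independent variables. It would also make a harmful change harder to detect.

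**Conclusion.** The point holds as a minor one. Section 9.4 commits to about 28 to 40 unadjusted tests, with the range set by an unlisted set of ABG values, and to no interval for change. At least one chance finding is more likely than not if nothing changes, but not if most variables do. The figures assume a 0.05 level, complete data in 20 patients and a within-patient correlation of 0.5.

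The missing intervals matter more than the test count and depend on none of the error-rate assumptions. With 20 pairs or fewer, a mean change can be non-significant while its interval reaches about half an SD of the change or more to either side. A reader should not go further and conclude that the primary result or the early-termination rule is compromised, since neither uses these tests.

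**What to change.** In section 9.4:

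1. List the ABG values to be analysed and say whether blood pressure is systolic, diastolic or both.
2. For every variable and time, report the mean change from baseline (or the Hodges–Lehmann estimate) with its 95% confidence interval and the number of pairs, as the main result.
3. Label any accompanying p-values exploratory and unadjusted, and state the rule for choosing the t-test or the Wilcoxon test.

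Naming one key contrast in advance is optional. So is Holm, with the limits noted above.

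The cost is a few lines of SAP text and slightly more output, with no extra patients or data. The downside is that no secondary result can be presented as confirmatory.

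### Section 9.4 names a log-rank test and chi-square/Fisher tests in a single-arm trial without defining what is compared

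*Combined protocol and SAP*

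**What the plan says.** The synopsis describes the design as "Prospective, single-arm, interventional pilot study" and gives the size as "20 patients (interim analysis after 10 enrollees; final analysis planned on 20"). The primary objective in 3.1 is to "Evaluate the incidence of intervention failure", where failure means intubation or excessive sedation (RASS ≤ -3).

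Section 9.4 lists three kinds of secondary analysis:

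- Continuous variables get paired tests, and the comparison is stated: each time point against baseline.
- Intubation and excessive sedation get "Chi-square or Fisher's exact test", with no comparison stated.
- The third item reads "Time-to-intubation: Kaplan–Meier curve with log-rank test", again with no comparison stated.

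Three other sections bear on the secondary part of this point:

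- 9.1: "Assuming baseline NIV failure/intubation rate of 50%, a 30% absolute reduction requires 20 patients for 80% power", at two-sided alpha 0.05.
- 9.2: the ITT set is "All enrolled patients who received any study intervention".
- 9.3: the failure proportion in the ITT set, with a "95% confidence interval (CI) using Wilson's method". It gives no reference value or threshold.

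**The concern.** The log-rank test compares survival curves between groups, or one curve with a reference curve. Chi-square and Fisher tests in their usual form compare proportions between groups. A single-arm trial supplies such groups only if the plan defines them, and this plan does not. The analyst would have to choose the groups, possibly after seeing the data, and any p-value would then answer a question that no objective in 3.1 or 3.2 asks.

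There is a lesser gap in the primary analysis. Section 9.1 speaks of power to detect a fall from 50%, while 9.3 only estimates a proportion. If the report later says that the assumed reduction was or was not shown, the rule behind that statement will not have been fixed beforehand.

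**Working it through.** **Is a comparison defined anywhere?** The candidates in the documents are:

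- *Arms:* one only (synopsis).
- *ITT and per-protocol sets (9.2):* overlapping analysis sets, not groups to compare.
- *Intubation crossed with excessive sedation:* a table can be formed, but neither 3.1 nor 3.2 asks about that association.
- *Baseline variables (section 7):* vital signs, ABG, RASS and VAS could be split into groups, but no split is prespecified.
- *One-sample chi-square against 50%:* possible for intubation using the rate in 9.1, but 9.4 does not refer to it, and the documents give no reference rate for excessive sedation.
- *Reference survival curve for the log-rank test:* none given.

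**Reproducing the sample size in 9.1.** Inputs from 9.1: p0 = 0.50; p1 = 0.50 − 0.30 = 0.20; power 80%; two-sided alpha 0.05.

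One-sample formula:
n = [1.960·√(0.5·0.5) + 0.8416·√(0.2·0.8)]² / 0.3² = (0.980 + 0.3366)² / 0.09 = 19.26, rounded up to **20**. This matches the plan.

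Two-group formula, per arm, pooled proportion 0.35:
n = [1.960·√(2·0.35·0.65) + 0.8416·√(0.25 + 0.16)]² / 0.09 = 38.5, rounded up to 39 per arm, or 78 in total. This does not match. Section 9.1 is therefore a one-sample calculation.

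**How the planned interval reads against 50%.** Wilson 95% CI, with z = 1.960:
[p̂ + z²/2n ± z·√(p̂(1−p̂)/n + z²/4n²)] / (1 + z²/n)

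| Failures | Wilson 95% CI | Upper limit below 50%? |
|---|---|---|
| 5/20 | 11.2% to 46.9% | yes |
| 6/20 | 14.5% to 51.9% | no |
| 5/19 | 11.8% to 48.8% | yes |
| 6/19 | 15.4% to 54.0% | no |

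The one-sample chi-square against 50% has the same cut-off at n = 20:

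- 5/20: (5−10)²/10 + (15−10)²/10 = 5.0, p = 0.025
- 6/20: 1.6 + 1.6 = 3.2, p = 0.074

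The exact binomial test gives p = 0.041 at 5/20, so it agrees there as well. With a cut-off of 5 or fewer at n = 20:

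- lower-tail error at a true 50%: P(X ≤ 5) = 21,700/2²⁰ = 2.1%
- power at a true 20%: P(X ≤ 5) = 80.4%

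**Why the rule would need naming.** The ITT set counts only treated patients, so one enrolled but untreated patient leaves n = 19. At n = 19:

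- Wilson rule (5 or fewer): lower-tail error 16,664/2¹⁹ = 3.2%, above the nominal 2.5%. Doubled, it is 6.4%, above the alpha in 9.1.
- Exact test: p = 0.064 at 5/19, so it needs 4 or fewer (lower-tail error 5,036/2¹⁹ = 1.0%).
- Power at a true 20%: 83.7% with 5 or fewer, 67.3% with 4 or fewer.

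**The case against.** The strongest reply on 9.4 is that the tests are not impossible. Baseline measurements could be dichotomised and crossed with intubation, and patients could even be split by excessive sedation for a log-rank test, although grouping by a post-baseline event is poor practice. This stands as far as it goes. A reader might infer that the tests cannot be run at all, but the documents support only that the comparison is unspecified. That is still a defect, because choosing groups after the fact is what a prespecified plan is meant to prevent.

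On 9.3, the reply is that a pilot whose objective is to estimate incidence needs no success rule, and that a proportion with a Wilson interval answers the objective. This also stands, so the 9.3 part is optional. A reader might infer that the missing rule invalidates the primary analysis or the sample size. It does not: the estimate and interval can be computed as planned, and N = 20 reproduces.

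Nor do the documents support requiring the Wilson rule and excluding the exact test. The two agree at n = 20, and at n = 19 it is the exact test that keeps within the alpha in 9.1.

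Finally, the 50% in 9.1 is described as a rate of NIV failure/intubation, whereas the primary composite also counts RASS ≤ -3. Comparing the composite with 50% without comment would mix endpoints. Every intubation is also a composite event, so a composite result below 50% carries over to intubation. The 80.4% power, however, holds only if the endpoint used in the rule has a true rate of 20%.

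**Conclusion.** The point holds as a minor one. In 9.4 the log-rank and chi-square/Fisher tests do not fit the single-arm design as written, because no comparison is defined for them. No numerical harm can be attached to this: it affects secondary outcomes only, and leaves the primary estimate, its interval and N unchanged.

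The mismatch between 9.1 and 9.3 is secondary. It matters only if the sponsor intends to draw a conclusion against 50%. In that case the choice of rule can decide the result at 5 failures of 19, but not at n = 20. The n = 19 case assumes one enrolled patient who is never treated. The figures assume a fixed reference of 50% and ignore the interim look.

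**What to change.** **In 9.4 (recommended):**

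- Replace the chi-square/Fisher tests with the count, proportion and Wilson 95% CI for intubation and for excessive sedation.
- Report the Kaplan–Meier curve for time to intubation with its 95% CI, and delete the log-rank test.

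**In 9.3 (optional, if a comparison with 50% is wanted):**

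- Prespecify one rule, either the Wilson upper limit below 50% or the exact binomial test.
- State whether the 50% applies to intubation alone or to the composite.
- State the cut-off if the ITT denominator is not 20. If the Wilson rule is chosen, note its 3.2% lower-tail error at n = 19.

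**Cost:** wording only. Sample size, data collection and the primary analysis stay as they are. The small downside is that intubation, excessive sedation and time to intubation carry no p-values.

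### Section 9.4 sets no horizon and no rule for discharge or death in the time-to-intubation curve; if both are censored over full follow-up, Kaplan–Meier can overstate the proportion intubated

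*Combined protocol and SAP*

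**What the plan says.** The documents describe a study that is "Prospective, single-arm, interventional pilot study", with 20 patients. The Duration row of the synopsis (section 1) gives "24 hours of sedation monitoring; follow-up until discharge or intubation".

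Section 9.4 gives the event-time analysis in one line: "Time-to-intubation: Kaplan–Meier curve with log-rank test". It states no time origin, no horizon, no censoring rule and no competing event. The same section lists intubation as a categorical outcome in its own right, separate from excessive sedation.

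The primary endpoint in section 3.1 is a composite, "defined as either requirement for endotracheal intubation or occurrence of excessive sedation". Section 9.3 reports it as a simple proportion: "Calculate proportion of intervention failures in ITT population", with a Wilson interval. Section 3.2 sets assessments "at baseline, 2, 6, 12, and 24 hours", and the table in section 7 schedules the check for intervention failure at 2, 6, 12 and 24 h.

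**The concern.** Over the follow-up in the synopsis, every surviving patient who is neither intubated nor lost leaves observation by going home. Kaplan–Meier by default censors anyone who leaves without the event, and it assumes that this person has the same later risk as those still observed. A patient discharged because the exacerbation resolved does not have the intubation risk of one still on the ward, and a patient who has died cannot be intubated. Both are competing events.

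The effect has one direction. Before any patient leaves, each intubation adds 1/20 to the curve. Each discharge or death then shrinks the risk set while the survival estimate stays put, so each later intubation adds more than 1/20. With 20 patients, a single late intubation can be a large step.

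At stake is the consistency of section 9.4 with itself. It asks for two summaries of the same event, a curve and a proportion, and they may not match. Section 9.1 is built on a fall from 50% by 30 points, to 20%. A trial that saw exactly 20% intubated could show a curve ending above 30%.

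**Working it through.** **Inputs from the documents.** N = 20; reference rate 50%; absolute reduction 30 points, so 20%; two-sided alpha 0.05; power 80% (section 9.1). Follow-up ends at discharge or intubation (section 1). The documents give no intubation or discharge times, so all times and hazards below are assumptions.

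**1. The plan's own figure.** The one-sample formula is n = (z₀.₉₇₅√(p₀q₀) + z₀.₈₀√(p₁q₁))² / (p₀ − p₁)². With p₀ = 0.5 and p₁ = 0.2 it gives (1.960 × 0.5 + 0.842 × 0.4)² / 0.09 = 19.26, so 20. The stated N reproduces, and this point does not touch it.

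**2. Fixed examples, 4 of 20 intubated (crude 20%).** Discharges are censored, and 1−KM is one minus the product of (1 − 1/number at risk) over the intubations.

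- All 4 before any discharge: 1 − 16/20 = 20.0%.
- 3 early, 1 after 8 of the 16 discharges (9 at risk): 1 − (17/20)(8/9) = 24.4%.
- 2 early, 2 after 8 of the 16 discharges (10, then 9 at risk): 1 − (18/20)(9/10)(8/9) = 28.0%.
- 3 early, 1 when 5 remain: 1 − (17/20)(4/5) = 32.0%.
- 3 early, 1 when 4 remain: 1 − (17/20)(3/4) = 36.25%.
- The last patient at risk is intubated: 100%.

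With discharge as a competing event and complete follow-up, the cumulative incidence ends at 4/20 = 20.0% in every case.

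**3. Constant hazards after day 1, read at day 14.** Assume 15% intubated in the first 24 h.

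- Then 2%/day intubation and 15%/day discharge. 1−KM: 1 − 0.85·exp(−0.02 × 13) = 34.5%. Cumulative incidence: 0.15 + 0.85(0.02/0.17)(1 − exp(−0.17 × 13)) = 23.9%. Excess 10.6 points.
- Then 1%/day and 20%/day. By the same formulas, 25.4% against 18.8%. Excess 6.6 points.

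**4. Simulation over a range of timings.** N = 20, true intubation risk 20%, 4,000 replicates per row, exponential intubation times, gamma (shape 4) discharge times, no deaths or losses. Discharge is censored when it occurs.

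| Median intubation / discharge (h) | Full follow-up: mean 1−KM | Mean crude | Trials identical | 24 h horizon: mean 1−KM | Mean crude | Trials identical |
|---|---|---|---|---|---|---|
| 6 / 120 | 19.9% | 19.9% | 91.8% | 18.8% | 18.8% | 97.8% |
| 12 / 120 | 20.1% | 19.7% | 66.4% | 15.0% | 15.0% | 96.8% |
| 24 / 120 | 22.8% | 20.0% | 32.0% | 10.0% | 10.0% | 97.1% |
| 48 / 120 | 36.6% | 20.1% | 10.5% | 5.7% | 5.7% | 97.8% |
| 72 / 120 | 52.8% | 19.8% | 5.6% | 4.1% | 4.1% | 98.5% |
| 24 / 72 | 31.0% | 19.9% | 14.8% | 10.1% | 10.0% | 86.1% |

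The full-follow-up means include any trial in which the last patient at risk is intubated and the curve jumps to 100%. With a true risk of 50% the pattern is the same: 50.2% against 50.1% at 6 / 120 h, and 88.3% against 50.0% at 72 / 120 h. At 24 h the largest mean gap in any run is 0.2 points (25.1% against 24.9%).

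**The case against.** The strongest reply is that no text says discharged patients are censored or that the curve runs past 24 h. Sedation is monitored for 24 h and failure is checked only up to 24 h, so a 24 h curve is a natural reading. On that reading the excess is negligible. Keeping discharged patients at risk to a fixed horizon is also compatible with Kaplan–Meier and removes the excess from discharge. All of this stands, and it is why the point is conditional. It does not close the gap, because the only end of follow-up that the plan states is discharge or intubation, and neither safeguard is written down.

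Three stronger readings are tempting, and the documents support none of them.

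- A reader might infer that the curve must be biased. It need not be: without an intubation after a discharge or death, the curve and the crude proportion are identical. Large excesses need late intubations, whose timing is assumed here.
- A reader might expect the curve to agree with section 9.3. That proportion also counts RASS of −3 or below, so an intubation-only curve by either method can differ from it for that reason alone.
- A reader might suppose that the curve will be judged against 50%. Section 9.1 uses that figure to size the study, and no text compares the curve with it.

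It is also fair to say that time-to-intubation is not among the secondary objectives in the synopsis or section 3.2. It appears only in section 9.4.

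**Conclusion.** The point holds as a gap in specification with a conditional bias. The plan names an estimator whose validity depends on a horizon and on a rule for discharge and death, and it gives neither. With both events censored over full follow-up, 1−KM cannot fall below the crude proportion intubated. The excess runs from nil (all intubations before the first discharge or death) through 4 to 8 points (one or two of four after half the discharges) to 12 points or more (one of four when five or fewer remain). Within 24 h it averaged at most 0.2 points in the runs above.

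These sizes rest on assumed times and hazards. The direction does not, provided that follow-up is otherwise complete. The correction is worth making because it is cheap, but the consequences are limited to a secondary analysis.

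**What to change.** In section 9.4, replace the Kaplan–Meier curve with the cumulative incidence (Aalen–Johansen) of intubation. Treat discharge alive and death without intubation as competing events, censor only true loss or withdrawal, and state the time origin and horizon. With complete follow-up the curve then ends at the crude proportion intubated in the same section.

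Alternatively, restrict the curve to a stated 24 h horizon, keep any earlier discharges at risk to 24 h, and say how a death without intubation before 24 h is handled.

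The cost is one amended SAP sentence and the times of intubation, discharge and death on the CRF. No extra patients or visits are needed. The 24 h option has the further drawback that it does not describe later intubations.

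Two separate gaps in the same analysis can be settled in that amendment: the log-rank test has no comparison group in a single-arm study, and the plan does not say how patients whose sedation was stopped for RASS of −3 or below enter the curve.
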